Stop the nivolumab infusion, begin an IV infusion of normal saline, (at approximately 40cc/hour but adjusted according to the clinical situation to ensure stabilization of blood pressure) and treat the subject with diphenhydramine 50 mg IV (or equivalent) and/or acetaminophen 325 to 1000 mg; remain at bedside and monitor subject until resolution of symptoms. Corticosteroid or bronchodilator therapy may also be administered as appropriate. If the infusion is interrupted, then restart the infusion at 50% of the original infusion rate when symptoms resolve; if no further complications ensue after 30 minutes, the rate may be increased to 100% of the original infusion rate. Monitor subject closely. If symptoms recur then no further nivolumab will be administered at that visit. Administer diphenhydramine 50 mg IV, and remain at bedside and monitor the subject until resolution of symptoms. The amount of study drug infused must be recorded on the case report form (CRF). The following prophylactic premedications are recommended for future infusions: diphenhydramine 50 mg (or equivalent) and/or acetaminophen 325 to 1000 mg should be administered at least 30 minutes before additional nivolumab administrations. If necessary, corticosteroids (recommended dose: up to 25 mg of IV hydrocortisone or equivalent) may be used.

For Grade 3 or Grade 4 symptoms [Severe reaction, Grade 3: prolonged (i.e. not rapidly responsive to symptomatic medication and/or brief interruption of infusion); recurrence of symptoms following initial improvement; hospitalization indicated for other clinical sequelae (e.g. renal impairment, pulmonary infiltrates), Grade 4: life-threatening; pressor or ventilatory support indicated]:

Immediately discontinue infusion of nivolumab. Begin an IV infusion of normal saline, (at approximately 40cc/hour but adjusted according to the clinical situation to ensure stabilization of blood pressure) and treat the subject as follows: Recommend bronchodilators, epinephrine 0.2 to 1 mg of a 1:1,000 solution for subcutaneous administration or 0.1 to 0.25 mg of a 1:10,000 solution injected slowly for IV administration, and/or diphenhydramine 50 mg IV with methylprednisolone 100 mg IV (or equivalent), as needed. Subject should be monitored until the investigator is

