comfortable that the symptoms will not recur. Nivolumab will be permanently discontinued. Institutional guidelines will be followed for the treatment of anaphylaxis. Remain at bedside and monitor subject until recovery from symptoms. In the case of late-occurring hypersensitivity symptoms (e.g. appearance of a localized or generalized pruritus within 1 week after treatment), symptomatic treatment may be given (e.g. oral antihistamine or corticosteroids).

For further details regarding dose-calculation of nivolumab, preparation and dispensing of nivolumab, administration of nivolumab please see the dosing procedure manual.

5.10.3 Nivolumab dose delay for immune-oncology drug-related adverse events, clinically significant in the opinion of the investigator

Nivolumab administration should be delayed for the following drug-related AEs:

- Any Grade >2 non -skin AE, except that
 - Grade 2 fatigue or laboratory abnormalities do not require delay, however
 - ◆ For a subject with baseline AST, ALT, or total bilirubin within normal limits, delay dosing for drug-related Grade >2 values
- Any Grade 3 skin AE, or Grade 3 laboratory abnormality, with the following exceptions:
 - Grade 3 lymphopenia or leukopenia does not require dose delay.
 - If a subject has Grade 1 baseline AST, ALT, or total bilirubin, delay dosing for drug-related Grade 3 toxicity
- Any AE, laboratory abnormality, or intercurrent illness, which in the judgment of the investigator, warrants delaying the dose of study medication.
- Nivolumab dose reductions are not permitted in this study (only dose delays when indicated).

Detailed management algorithms for immune-oncology drug-related adverse events (including gastrointestinal, renal, pulmonary, hepatic, endocrine, skin and neurological) are provided in Appendix E. These general guidelines constitute guidance to the Investigator and may be supplemented by discussions with the Medical Monitor representing the Sponsor. If the criterion to resume treatment is met, the subject should restart treatment at the next scheduled time-point per protocol.

Criteria to Resume Treatment:

Subjects may resume treatment with study drug when the drug-related AE(s) resolve to Grade ≤1 or baseline value, with the following exceptions:

- Subjects may resume treatment in the presence of Grade 2 fatigue
- Subjects who have not experienced a Grade 3 drug-related skin AE may resume treatment in the presence of Grade 2 skin toxicity

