- Subjects with baseline Grade 1 AST/ALT or total bilirubin who require dose delays for reasons other than a 2-grade shift in AST/ALT or total bilirubin may resume treatment in the presence of Grade 2 AST/ALT OR total bilirubin
- Subjects with combined Grade 2 AST/ALT AND total bilirubin values meeting discontinuation parameters (Discontinuation Section below) should have treatment permanently discontinued
- Drug-related pulmonary toxicity, diarrhea, or colitis, must have resolved to baseline before treatment is resumed
- Drug-related endocrinopathies adequately controlled with only physiologic hormone replacement may resume treatment

If the criteria to resume treatment are met, the subject should restart treatment at the next scheduled timepoint per protocol. However, if the treatment is delayed past the next scheduled timepoint per protocol, the next scheduled timepoint will be delayed until dosing resumes.

If treatment is delayed > 6 weeks, the subject must be permanently discontinued from study therapy, except as specified in discontinuation section.

Nivolumab Discontinuation Criteria:

Treatment should be permanently discontinued for the following:

- Any Grade 2 drug-related uveitis or eye pain or blurred vision that does not respond to topical therapy and does not improve to Grade 1 severity within the re-treatment period OR requires systemic treatment
- Any Grade 3 non-skin, drug-related adverse event lasting > 7 days, with the following exceptions for drug-related laboratory abnormalities, uveitis, pneumonitis, bronchospasm, diarrhea, colitis, neurologic adverse event, hypersensitivity reactions, and infusion reactions:
 - Grade 3 drug-related uveitis, pneumonitis, bronchospasm, diarrhea, colitis, neurologic adverse event, hypersensitivity reaction, or infusion reaction **of any duration** requires discontinuation
- Grade 3 drug-related laboratory abnormalities do not require treatment discontinuation except those noted below:
 - Grade 3 drug-related thrombocytopenia > 7 days or associated with bleeding requires discontinuation
 - Any drug-related liver function test (LFT) abnormality that meets the following criteria require discontinuation:
 - AST or ALT > 8 x ULN
 - Total bilirubin > 5 x ULN
 - Concurrent AST or ALT > 3 x ULN and total bilirubin > 2 x ULN

- Any Grade 4 drug-related adverse event or laboratory abnormality, except for the following events which do not require discontinuation:

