 - Isolated Grade 4 amylase or lipase abnormalities that are not associated with symptoms or clinical manifestations of pancreatitis and decrease to < Grade 4 within 1 week of onset.
 - Isolated Grade 4 electrolyte imbalances/abnormalities that are not associated with clinical sequelae and are corrected with supplementation/appropriate management within 72 hours of their onset
- Any dosing interruption lasting > 6 weeks with the following exceptions:
 - Dosing interruptions to allow for prolonged steroid tapers to manage drug-related adverse events are allowed. Prior to re-initiating treatment in a subject with a dosing interruption lasting > 6 weeks, the Investigator must be consulted. Tumor assessments should continue as per protocol even if dosing is interrupted
 - Dosing interruptions > 6 weeks that occur for non-drug-related reasons may be allowed if approved by the Investigator. Prior to re-initiating treatment in a subject with a dosing interruption lasting > 6 weeks, the Investigator must be consulted. Tumor assessments should continue as per protocol even if dosing is interrupted
- Any adverse event, laboratory abnormality, or intercurrent illness which, in the judgment of the Investigator, presents a substantial clinical risk to the subject with continued nivolumab dosing

5.11

Definition of Dose Limiting Toxicity (DLT)

Dose-Limiting Toxicity will be graded according to the NCI Common Toxicity Criteria version4.03. See NCI Common Toxicity Criteria for definitions of DLT by organ system.

- a) All \geq grade 3 drug-related, clinically significant non-hematologic toxicities will be considered DLTs. A study drug-related occurrence of an elevation in AST/ALT $> 3 \times$ ULN and concomitant Bilirubin of $> 2 \times$ ULN is a Dose Limiting Toxicity and patients meeting this criteria should be permanently discontinued from study treatment (nivolumab).
As the following are common events in patients with leukemia (> 50%), they will not be used for the definition of MTD and DLT, nor will they be reported as ADRs: low blood pressure due to dehydration requiring fluid replacement, abnormalities of LDH (lactate dehydrogenase) and alkaline phosphatase, disturbances in electrolytes (magnesium, phosphorus,

calcium), alopecia, nausea and vomiting (if manageable with supportive care measures).

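### Section 5.10.2 gives no single grade to a nivolumab infusion reaction that resolves and recurs on restart: its Grade 2 text implies later dosing, its Grade 3 text requires permanent discontinuation

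*Combined protocol and SAP*

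**What the plan says.** Section 5.10.2 (Treatment of nivolumab Related Infusion Reactions) sets out management by grade and asks for grading by CTCAE 4.03.

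- **Grade 2 paragraph.** The infusion is stopped and the patient is treated. If the infusion was interrupted, staff are told to "restart the infusion at 50% of the original infusion rate when symptoms resolve". A recurrence is then covered expressly: "If symptoms recur then no further nivolumab will be administered at that visit". The paragraph closes with premedication for later infusions, which "should be administered at least 30 minutes before additional nivolumab administrations". It makes no exception for a patient whose symptoms came back.
- **Grade 3 or 4 paragraph.** The printed description of Grade 3 includes "recurrence of symptoms following initial improvement; hospitalization indicated for other clinical sequelae". The stated action is "Nivolumab will be permanently discontinued".
- **Section 5.10.3, discontinuation criteria.** The list of Grade 3 drug-related events that end treatment finishes with "hypersensitivity reaction, or infusion reaction of any duration requires discontinuation".
- **Section 5.11, DLT definition.** Events of at least "grade 3 drug-related, clinically significant non-hematologic toxicities will be considered DLTs". Infusion reactions are not among the events that the section excludes.

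Section 5.10.2 also requires Grade 3 or 4 infusion reactions to reach the Medical Monitor within 24 hours. Section 12.3 monitors unacceptable Grade 3 or 4 toxicity attributable to nivolumab.

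**The concern.** The Grade 2 paragraph plans for one specific sequence: reaction, resolution, restart, recurrence. The Grade 3 description, in the next paragraph, names a return of symptoms after improvement as one of its features. Two clinicians who both follow the text could therefore act differently on the same event. One stops for the day and premedicates at the next visit, and the other withdraws nivolumab for good.

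Patient safety comes first here, because the decision is made at the bedside. The grade is also an input to three other parts of the plan: expedited reporting, the 3+3 dose decision in phase I, and the Bayesian toxicity rule in phase II. If the grade depends on which paragraph staff read, so may those inputs.

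**Working it through.** **Step 1. The two rules applied to one event.** A patient reacts at Grade 2, the infusion is stopped, symptoms resolve, the infusion restarts at 50% of the original rate, and symptoms return.

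| Question | Grade 2 paragraph, 5.10.2 | Grade 3 text, 5.10.2 and 5.10.3 |
|---|---|---|
| Does the event fit? | Yes: recurrence after restart is provided for | Yes: symptoms improved, then recurred |
| Rest of this visit | No more nivolumab | No more nivolumab |
| Later visits | Premedication recommended before further infusions | None: permanent discontinuation |
| Medical Monitor within 24 hours because of grade | No | Yes |
| Grade high enough for a DLT (5.11) | No | Yes, with conditions |
| Grade high enough for the phase II rule (12.3) | No | Yes, with conditions |

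The two columns agree on the current visit and part from the next visit onward. No sentence says that a recurrence is re-graded, or that it stays at Grade 2.

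**Step 2. Conditions on the DLT consequence.** Section 5.11 requires the event to be drug-related and clinically significant, and sections 5.2 and 12.2 count first-cycle events only. Nivolumab starts on day 24 ± 2 of a cycle of about 28 to 35 days and is given about every 2 weeks. The nominal second dose falls on day 24 + 14 = 38, after the cycle ends. With the earliest start and the 12-day minimum interval in section 13.1.6, it falls on day 22 + 12 = 34. The observation period of about 3 weeks from the first dose covers doses at 0 and 14 days. So only the first one or two infusions matter, in at most 12 phase I patients (section 12.2).

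Within that window, one change of grade can move a cohort from 0/3 to 1/3 (up to 3 more patients at that level) or from 1/6 to 2/6 (level closed). Any single DLT would do the same.

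**Step 3. Conditions on the phase II consequence.** The event counts only if judged unacceptable and attributable to nivolumab. With the beta(0.2, 1.8) prior and k events in n patients, the posterior is beta(0.2 + k, 1.8 + n − k), and the trial stops if P(rate > 0.10) > 0.95.

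- n = 5: k = 2 gives beta(2.2, 4.8) and P = 0.920, so continue; k = 3 gives beta(3.2, 3.8) and P = 0.990, so stop.
- n = 10: k = 3 gives beta(3.2, 8.8) and P = 0.933, so continue; k = 4 gives beta(4.2, 7.8) and P = 0.987, so stop.

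These reproduce the 3-of-5 and 4-of-10 boundaries in Table 13.3; the remaining boundaries reproduce as well. The rule itself is sound. A recurrent reaction could supply one of those events, depending on its grade and on the two judgements.

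**Step 4. Reporting.** Section 10.1 already sends every SAE to the drug supplier within 24 hours, related or not. The grade therefore makes its main difference to the 24-hour duty for reactions that are not serious.

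**Step 5. Frequency.** Section 5.10.2 describes infusion reactions as unlikely, and no section gives a rate of reactions or of recurrences. A change in stopping or escalation probability cannot be derived from the documents, and none is claimed.

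**The case against.** The strongest answer is that the paragraphs can be read in sequence. The Grade 2 description requires a prompt response to symptomatic treatment. A reaction that comes back no longer fits it and moves to Grade 3. Stopping for the visit is then only the immediate instruction (no second restart, antihistamine, continued monitoring), and the Grade 3 text governs what follows. Stopping today is compatible with stopping for good. The premedication sentence also serves patients who restarted without trouble.

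This reading is possible, and part of it stands: no sentence says outright that a patient whose symptoms recurred may be re-treated. A reader might infer that the protocol orders continuation. It does not. Continuation is implied by limiting the stop to that visit and by recommending premedication afterwards without exception. But the re-grading is not stated either, and under it the limit to one visit has little purpose.

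Section 5.10.2 also lets its treatment recommendations be adapted to institutional standards. That does not settle the grade, and the discontinuation criterion in 5.10.3 carries no such allowance. Requiring CTCAE grading does not help either, because the protocol prints its own Grade 3 description without reconciling it with the restart instruction.

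A reader might further infer that every such recurrence is a DLT or counts toward stopping phase II. The documents do not support that: both depend on the timing and clinical judgements set out in the working.

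**Conclusion.** Wrong as written. In the current text, one foreseeable event meets both the Grade 2 recurrence instruction and the printed Grade 3 description. The first implies later dosing and the second forbids it, and nothing says which prevails. This rests on the wording alone and on no assumed figure.

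The practical size is small. Few patients are likely to be affected, and the effects on DLT status, toxicity monitoring and reporting are conditional. The EFS endpoint definition, the sample size and the stopping boundaries are untouched. The point still deserves correction because it concerns whether a patient who has reacted twice at one visit receives the drug again, and staff need one instruction at that moment.

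**What to change.** Reconcile three places: the Grade 2 restart paragraph and the Grade 3 description in 5.10.2, and the discontinuation criteria in 5.10.3. State the one grade that a recurrence after restart receives. Then make re-treatment or discontinuation, 24-hour Medical Monitor reporting, DLT assessment under 5.11 and the toxicity count under 12.3 follow from that grade, each with its existing conditions. The sponsor decides which grade; this review takes no position on the clinical rule.

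The cost is one or two sentences in 5.10.2 with a cross-reference to 5.10.3. No procedure, visit or data item is added, and no operating characteristics need to be recomputed.

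### As supplied, section 5.10.3 starts the grade-based nivolumab delay above Grade 2, which contradicts the section's own Grade 2 exemption and liver tiers and leaves diarrhea, colitis and pneumonitis with no grade-based delay level before permanent discontinuation

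*Combined protocol and SAP*

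**What the plan says.** The delay list in section 5.10.3 has three working parts.

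- **Non-skin events.** Delay for "Any Grade >2 non -skin AE, except that" two things follow. First, "Grade 2 fatigue or laboratory abnormalities do not require delay, however". Second, as a qualification of that exemption, "For a subject with baseline AST, ALT, or total bilirubin within normal limits, delay dosing for drug-related Grade >2 values".
- **Skin and laboratory events.** "Any Grade 3 skin AE, or Grade 3 laboratory abnormality, with the following exceptions". One of the items beneath it is "If a subject has Grade 1 baseline AST, ALT, or total bilirubin, delay dosing for drug-related Grade 3 toxicity".
- **Judgment.** "Any AE, laboratory abnormality, or intercurrent illness, which in the judgment of the investigator, warrants delaying the dose of study medication".

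The section heading limits the list to events that are "clinically significant in the opinion of the investigator". Nivolumab may be delayed but not reduced.

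Treatment may resume "when the drug-related AE(s) resolve to Grade ≤1 or baseline value", with stated exceptions, one of which is Grade 2 fatigue. Pulmonary toxicity, diarrhea and colitis must return to baseline first. Another resume item concerns patients with Grade 1 liver values at baseline, and refers to a shift of two grades as a reason for their delay.

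Under the discontinuation criteria, drug-related diarrhea, colitis or pneumonitis of Grade 3 ends nivolumab permanently whatever its duration. Grade 4 drug-related events do the same, apart from exceptions for isolated amylase, lipase and electrolyte abnormalities.

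**The concern.** An exemption for Grade 2 makes sense only under a rule that would otherwise catch Grade 2. A rule for Grade >2 does not. The qualification for liver tests likewise reads as a stricter rule for patients who start with normal values, yet as supplied it is no stricter than the rule for patients who start at Grade 1. Both features suggest that Grade ≥2 was meant.

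Delay is the only step short of stopping nivolumab, because dose reduction is not allowed. Section 5.9 makes two-weekly maintenance dosing for up to a year the default, interrupted only for toxicity. A physician who consults the list for a patient with drug-related Grade 2 colitis or pneumonitis finds no grade that calls for a hold, and the next grade-based step is permanent discontinuation at Grade 3. Patients with the same Grade 2 event could then be handled differently by different physicians.

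**Working it through.** The plan gives no figure to reproduce. The check takes each rule in section 5.10.3 and applies it under the two possible symbols.

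| Rule | Read as >2 | Read as ≥2 |
|---|---|---|
| Non-skin grades that trigger delay (non-fatal grades) | 3, 4 | 2, 3, 4 |
| Grade 2 fatigue/laboratory exemption | removes nothing | removes Grade 2 fatigue and laboratory values |
| Liver delay starts, normal baseline | Grade 3 | Grade 2 |
| Liver delay starts, Grade 1 baseline | Grade 3 | Grade 3 |
| Rise from baseline at which liver delay starts (normal; Grade 1) | 3 − 0 = 3; 3 − 1 = 2 | 2 − 0 = 2; 3 − 1 = 2 |
| Diarrhea, colitis, pneumonitis: grades delayed but not discontinued | {3, 4} minus {3, 4} = none | {2, 3, 4} minus {3, 4} = {2} |

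**Exemption.** Under >2 the set of Grade 2 events caught by the trigger is empty, so there is nothing to exempt.

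**Liver tiers.** Under >2 the two tiers start at the same grade, a difference of 3 − 3 = 0. The normal-baseline item also adds no trigger at Grade 3, because the next bullet already lists Grade 3 laboratory abnormalities. Under ≥2 the tiers differ by 3 − 2 = 1 grade, and both start at a rise of two grades, which matches the two-grade shift in the resume criteria.

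**Bowel and lung events.** For diarrhea, colitis and pneumonitis, every grade that triggers delay under >2 also triggers discontinuation. The requirement that diarrhea or colitis return to baseline before restart therefore has no grade-based hold to end; it can follow only a discretionary one. Pulmonary toxicity is a wider term than pneumonitis, so the statement is limited to pneumonitis.

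**Exposure.** Dosing every 2 weeks for up to 1 year gives at most about 52 / 2 = 26 doses per patient at which the list is consulted. The delay limit of 6 weeks equals 6 / 2 = 3 scheduled doses.

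**The case against.** The strongest objection is that the whole point turns on one character, printed twice, in text read from a PDF. No ≥ sign survives anywhere in the supplied section 5.10.3, and the spacing of the quoted line is irregular. Every contradiction listed above would also appear if the source prints ≥2 and the bar was lost. Against this, ≤ survives in the same section's resume rule, and ≥ survives in the eligibility criteria (section 4.0) and in the dose-limiting toxicity definition (section 5.11), so such symbols were not lost throughout. That does not settle how this symbol was set. The objection stands as a reason to check the source before calling this an error in the plan.

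A reader might infer that Grade 2 colitis or pneumonitis meets no delay trigger at all, or must be dosed through. The documents do not support that. The judgment item is itself a listed trigger for an event of any grade, section 5.3 allows delays after discussion with the principal investigator, and section 5.10.3 refers gastrointestinal and pulmonary events to Appendix E, which may advise a hold at Grade 2. What is missing is a grade-based trigger.

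A reader might also object that a new Grade 2 event does not trigger a delay while a patient held at Grade 3 generally cannot restart at Grade 2. That is not a defect. The skin rule works this way under either symbol: Grade 2 skin toxicity triggers no grade-based delay, but a patient who has had a Grade 3 skin event may not restart at Grade 2.

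Finally, redundancy with the Grade 3 laboratory bullet is weak evidence alone, because the Grade 1-baseline item repeats that bullet even under ≥2. The empty exemption and the unequal shifts carry more weight.

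**Conclusion.** On the supplied text the delay rule contradicts its own section, and the point is worth fixing. Confidence is moderate because of the symbol. The size is one grade: the grade-based delay for non-skin events other than fatigue and laboratory values, and for liver values from a normal baseline, starts at Grade 3 where the rest of the section implies Grade 2. For diarrhea, colitis and pneumonitis this removes the only grade-based delay level before permanent discontinuation.

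The conclusion assumes that the source prints >2; if it prints ≥2, nothing remains. It makes no claim about Appendix E, which was not available. Nor does it claim that ≥2 would make a hold strictly mandatory: the heading's reference to investigator opinion and the advisory wording of the list leave room for judgment under either symbol. The liver discontinuation limits and the dose-limiting toxicity definition are unaffected. The documents give no incidence of Grade 2 immune events, so no count of affected patients is offered.

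**What to change.** Check the symbol in the source PDF. If it prints >2, change it to Grade ≥2 in both places in section 5.10.3: the non-skin trigger and the liver item for normal baselines. Grade 2 non-skin drug-related events other than fatigue and laboratory values, and Grade ≥2 liver values from a normal baseline, then become grade-based delay triggers. If it prints ≥2, no change is needed.

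The edit is two symbols, with no extra patients or procedures. The cost is some additional dose delays. A few may exceed the 6-week limit (three scheduled doses) and lead to permanent discontinuation unless an exception applies, such as a prolonged steroid taper.

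Separately, and whatever the symbol, section 5.5 sends the reader to section 6.10.3 for delay guidance. The table of contents lists only 6.1 under section 6, and the guidance is in 5.10.3. That pointer is a clerical correction and forms no part of this point.
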